Single-center, Prospective, Non-Randomized  
Control Clinical Trial of Retro - auricular Single - site  
Endoscopic Versus Open Surgery in Patients with  
Early Stage Papillary Thyroid Carcinoma

Study Protocol

Version date: January, 19, 2022

Official Title	Single-center, Prospective, Non-Randomized Control Clinical Trial of Retro - auricular Single - site Endoscopic Versus Open Surgery in Patients with Early Stage Papillary Thyroid Carcinoma
Brief Summary	The goal of this non randomized control clinical research study is to compare the cosmetic outcomes and efficiency of retro - auricular single - site endoscopic thyroid lobectomy and central lymph node dissection against conventional resection.
Conditions	Age: 18~70 years. Patients with early stage papillary thyroid carcinoma.
Outcome Measures	
 
● Primary Outcome Measure: postoperative cosmetic satisfaction scores
 
● Secondary Outcome Measures: 
 
➢ Cosmetic outcome: postoperative Vancouver Scar Scale
 
➢ Surgical outcomes: CRP level, SAA level, intraoperative blood loss, VAS pain score, Operative time.
 
➢ Clinicopathologic characteristics: tumor size, number of lymph nodes, the positive rate of lymph nodes.
 
➢ Complication: complication rates and types
 
 
 

Study Process	<pre> graph LR     A[early stage papillary thyroid carcinoma] --> B[1:1 Non-Randomized]     B --> C[RASSET group N=40]     B --> D[Open group N=40]     C --> E[Postoperative cosmetic satisfaction scores]     D --> E </pre>
Sample Size	80(40 VS 40)
Inclusion Criteria	
 
● Age 18-70 years old, no gender restrictions.
 
● Fine-needle aspiration cytology(FNA) confirmed papillary thyroid carcinoma(PTC).
 
● Early stage PTC (stage T1N0M0).
 
● Preoperative ultrasonography showed unilateral glandular lobe malignant tumor and the largest diameter was not more than 2cm, without cervical lymph node metastasis and extensive metastasis.
 
● Patients undergoing thyroid lobectomy and central lymph node dissection.
 
● Patients who have signed an approved Informed Consent.
 

Exclusion Criteria	
 
● Patients who do not accept case data collection for various reasons.
 
● The clinical data unfit this study (at the discretion of the investigator).
 
● Patients who have undergone neck surgery or radiotherapy before this trial.
 
● Patients who have uncontrolled hyperthyroidism.
 

Elimination Criteria	
 
● Patients who violated the requirements of the research protocol.
 
● The quality of data records is incomplete and inaccurate.
 
● Lost cases.
 

Study Completion	2023-06-30
Locations	1

Groups	RASSET group VS traditional open thyroid lobectomy group
Masking and Allocation	None (Open Label). Non-Randomized(patient decided his surgery approach).
Statistical Analysis Plan	
In this clinical study, the test level <math>\alpha</math> was set to be 0.05 on both sides; the test efficiency Power (ie, <math>1-\beta</math>) was selected as 0.8 (ie, type II error <math>\beta=0.2</math>); The sum standard deviation is <math>5.54\pm 1.75</math>, and the mean and standard deviation of the score of the cosmetic effect evaluation scale of the experimental group is expected to be <math>3.92\pm 1.41</math>. The 1:1 parallel control method is used, and the sample size calculation formula is based on the mean comparison of the two samples. According to the calculation of PASS software, this study requires a sample size of about 72 people (36 cases in each group). Considering the 10% dropout rate, the required sample size for each group is 40 cases, and a total of 80 cases in the two groups are required.
 
All analyses were performed using SPSS 26.0, and a <math>P</math> value less than 0.05 was considered significant. Normally distributed quantitative data are represented by mean (SD) [range]. Non-normally distributed quantitative data are represented by <math>M(Q_R)</math>. Comparison between groups was performed using the Mann-Whitney U test.
 
Categorical data are expressed as frequencies and percentages. Comparisons between groups were performed using the <math>\chi^2</math> test or Fisher's exact test.

## Study Protocol

### 1. Background

Thyroid cancer is one of the most common malignant tumors in the head and neck. Among it, papillary thyroid carcinoma accounts for about 70% of thyroid cancer. The degree of malignancy is low, but there is a tendency for multicentricity, and cervical lymph node metastasis occurs early. Due to the development of diagnosis technology, the amount of papillary microcarcinoma is getting higher and higher. At the same time, the change of aesthetic makes young women pursue a scarless neck.

Surgery is the first choice of treatments for early-stage thyroid cancer. Traditional open surgery tended to leave a long scar on the neck, which affects the cosmetic outcome. At present, many reported approaches, such as trans-areola approach, trans-axillary approach, trans-oral approach or some combined approaches, all have wider flap dissection or greater body trauma, and at the same time, these above approaches are difficult to achieve complete dissection of central lymph nodes.

Therefore, based on the experience of transauricular hairline endoscopic thyroidectomy, we established a new operative method-the Retro-auricular single-site endoscopic thyroidectomy (RASSET). The incision is only 3cm and located at the

posterior sulcus of the auricle, which can meet the cosmetic needs. Compared with other endoscopic approaches, the dissection area is small and the flap dissection is small, which may reduce the surgical trauma. The RASSET is easy to resect the upper pole of the thyroid gland, and can achieve complete dissection of the central lymph nodes. The article titled "A comparative study between retro - auricular single - site endoscopic thyroidectomy and transoral endoscopic thyroidectomy vestibular approach: a single - center retrospective analysis" has been published in "Chin J Surg". Guangdong Medical Information Research Institute recognized that there was no report of endoscopic thyroid surgery for this approach at home and abroad, and it also passed the new technology evaluation in the Sun Yat-sen University Cancer Center, and was recognized as an international leader.

**Figure 1. A:**Sun Yat-sen University Cancer Center Certificates(international innovation). **B:**Guangdong Medical Information Research Institute Certificates(no report of this approach).**C:**Zhonghua Wai Ke Za Zhi(a new approach).

**Figure 2. [name]'s authorization**

### 3. Study Eligibility

- Inclusion Criteria:
  - Age 18-70 years old, no gender restrictions.
  - Fine-needle aspiration cytology(FNA) confirmed papillary thyroid carcinoma(PTC).
  - Early stage PTC (stage T1N0M0).
  - Preoperative ultrasonography showed unilateral glandular lobe malignant tumor and the largest diameter was not more than 2cm, without cervical lymph node metastasis and extensive metastasis.
  - Patients undergoing thyroid lobectomy and central lymph node dissection.
  - Patients who have signed an approved Informed Consent.
- Exclusion Criteria:

- Patients who do not accept case data collection for various reasons.
- The clinical data unfit this study (at the discretion of the investigator) .
- Patients who have undergone neck surgery or radiotherapy before this trial.
- Patients who have uncontrolled hyperthyroidism.
- Withdrawal criteria:
 

(A withdrawal case refers to a patient who withdraws from treatment for various reasons in study. Patients with the following conditions will be withdrawn from investigational treatment.)

  - The patient himself or his legal representative requests to withdraw.
  - In the opinion of the investigator, the patient's continued participation in the study will be detrimental to his health.
- Elimination Criteria:
  - Patients who violated the requirements of the research protocol.
  - The quality of data records is incomplete and inaccurate.
  - Lost cases.

#### 4. Case Screening

- examination items

All cases must complete the following examination items before being considered for entry into this study. It is generally required to be completed within 7 days before treatment.

- Complete medical history and comprehensive physical examination, including symptoms, signs and specialist examination.
- Check items that must be done before routine treatment, including: Blood routine: neutrophil/lymphocyte ratio, Coagulation function: d-dimer, Serological tests: CRP, SAA, procalcitonin, calcium level, Thyroid function: TSH level, parathyroid hormone level, Thyroid ultrasonography, thyroid Computed tomography scan if necessary, Chest X-ray, abdominal ultrasonography, electrocardiogram.

[figure not shown]
**The above examinations are all routine preoperative examinations, which do not cause additional financial burden on patients.**

- Case screening

According to various examinations, those who meet the inclusion criterias are screened out. The patients entered the study after completing the required examinations and being evaluated according to the inclusion criterias. Then sign the informed consent form and get treatment.

#### 5. Study Process

Figure 3. flowchart

## 6. Surgical Technique

### ● Retro-auricular single-site endoscopic thyroidectomy (RASSET )

For the RASSET technique, in the beginning, patient was placed in a supine position with slight neck bending. When the lower pole of the thyroid gland was going to be dissected, the patient was placed in a supine position with slight neck extension. Mark the operation path on the surface. Slit the skin, subcutaneous tissue and superficial cervical fascia in turn. Expose the middle branch of the great auricular nerve and the sternocleidomastoid muscle under direct vision. The working space was created in the superficial layer of deep cervical fascia between the sternocleidomastoid muscle and the platysma muscle, which meets the principle of membrane anatomy. The area of flap dissection just includes the anterior cervical muscle and the anterior edge of the sternocleidomastoid muscle, which is so narrow to minimize the traumatic dissection. Pulling apart the anterior cervical muscle and the sternocleidomastoid muscle along the deep cervical fascia can fully expose the thyroid gland, the recurrent laryngeal nerve (RLN) and common carotid artery that are surrounded by the middle layer of deep cervical fascia and ensure that tumor and central lymph nodes en - bloc resection can be operated in the middle layer of deep cervical fascia to conform the natural anatomical region. For details, please refer to "A comparative study between retro - auricular single - site endoscopic thyroidectomy and transoral endoscopic thyroidectomy vestibular approach: a single - center retrospective analysis".

[figure not shown]

Figure 4. model and practical operation

- traditional open surgery

For traditional open surgery, the patient was placed in a supine position. A 4-6cm transverse incision was made. Subplatysmal flaps were dissected up to the thyroid cartilage and down to the sternal notch. The strap muscles were separated in the midline to expose the thyroid gland. Lateral dissection of the thyroid gland was performed. The middle thyroid vein was ligated. Superior thyroid vessels were individually ligated close to the thyroid gland. The RLN was identified and dissected near the inferior thyroid artery. Branches of the inferior thyroid vessels were ligated, preserving the lower parathyroid gland. Berry ligament was then dissected, and finally the isthmus was transected. The thyroid and central lymph nodes were resected. For details, please see "Clinical Practice and Skills in Head and Neck Oncology Surgery".

## 7. Outcome Measures

- Baseline Characteristics of Patients

Gender, Age, BMI, Tumor size, Pathological type, Tumor location, ASA grade.

- Postoperative Outcomes

- Cosmetic outcome: postoperative Vancouver Scar Scale 1 and 3 months from surgery, postoperative cosmetic satisfaction scores 1 month from surgery.
- Surgical outcomes: CRP level, SAA level, Drainage volume (ml), intraoperative blood loss, VAS pain score, Operative time.
- Clinicopathologic characteristics: tumor size, number of lymph nodes, the positive rate of lymph nodes.
- Complications: complication rates and types.

- Primary Outcome Measure: postoperative cosmetic satisfaction scores 3 months from surgery.

## 8. Code of Ethics

- Informed consent

Before each patient was enrolled in this study, the research investigators are responsible for a complete and comprehensive introduction to the surgical method of this study, its possible side effects and possible risks, and let patients know their rights, risks and benefits to be assumed. Patients should have signed informed consent before enrollment.

- Ethical norms and policies and regulations

This clinical trial must comply with the Declaration of Helsinki (2000 Edition), the Good Clinical Practice (GCP) promulgated by the SFDA, and related regulations. Before the start of the trial, the study could be started only after the protocol was approved by the ethics committee of the lead unit. Any modification of the trial protocol during clinical research should be reported to the ethics committee and filed.

- Obtaining ethics approval

Ethical approval has been obtained.

## 9. Quality Assurance

In order to ensure that this trial can be carried out in strict accordance with the clinical research protocol, during the entire process of the clinical trial, clinical investigators and clinical sponsors should behave in strict accordance with the requirements of the Good Clinical Practice for Drugs (GCP), and be sure to follow the trial procedures. Standardized, accurate test data, and reliable research conclusions. Specific requirements are as follows:

- Requirements for collaborators:

- Lectures on clinical programs, CRF filling, etc. are given to the researchers before the clinical start.
- Send clinical monitors to conduct on-site inspections.
- Ensure that the researchers can keep in touch with the researchers at any time by telephone or email.

- Requirements for researchers:

- Responsible for obtaining the "Informed Consent" signed by each subject or his agent.
- Complete the case report form (CRF) carefully as required.
- Regular visits.
- Completely maintain records of clinical records, and original medical records of subjects.

## 10. Data Processing and Preservation

- Case report form (CRF)

The case report form should be filled out by investigators, and the CRF form should be filled out in time to ensure accurate content and timely summary. Generally, the CRF form should not be altered. If there is an error that needs to be revised, it should be signed at the revised place. The CRF form is in triplicate, and after the trial is over, it will be handed over to the clinical team leader hospital, the sponsor and the trial hospital for preservation. Data entry was performed after the completed case report was reviewed by the clinical monitor. The contents of the case report form are no longer modified.

- Create a database

After receiving the CRF form, the statistician will verify the question by the researcher, and the researcher should answer and return as soon as possible. Statisticians will establish a database at the same time. After the database is reviewed, the data will be locked by the principal investigators, sponsors, statistician and clinical monitors. To ensure data security, irrelevant personnel cannot access and modify the data, and the data must be backed up.

- Storage of data

The researcher should keep the data intact. According to the principle of GCP in China, for the investigators or hospitals, the data storage should be more than 5 years.

## 11. Statistical analysis

Professional statisticians undertake statistical analysis tasks and participate in the whole process from experimental design, implementation to analysis and summary. After the study protocol and case report form are completed, a statistical analysis plan shall be formulated. After some necessary modifications shall be made during the study process as required, and a statistical analysis report shall be provided after the data analysis is completed.

- Sample size

In this clinical study, the test level  $\alpha$  was set to be 0.05 on both sides. the test efficiency Power (ie,  $1-\beta$ ) was selected as 0.8 (ie, type II error  $\beta=0.2$ ). The sum standard deviation is  $5.54\pm 1.75$ , and the mean and standard deviation of the score of the cosmetic effect evaluation scale of the experimental group is expected to be  $3.92\pm 1.41$ . The 1:1 parallel control method is used, and the sample size calculation formula is based on the mean comparison of the two samples. According to the calculation of PASS software, this study requires a sample size of about 72 people (36 cases in each group). Considering the 10% dropout rate, the required sample size for each group is 40 cases, and a total of 80 cases in the two groups are required.

- Statistical Analysis

All analyses were performed using SPSS 26.0, and a P value less than 0.05 was considered significant. Normally distributed quantitative data are represented by mean (SD) [range]. Non-normally distributed quantitative data are represented by M (QR) . Comparison between groups was performed using the Mann-Whitney U test. Categorical data are expressed as frequencies and percentages. Comparisons between groups were performed using the  $\chi^2$  test or Fisher's exact test.

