# Appendix

## Appendix 1 Cosmetic satisfaction questionnaire

Q1. How satisfied are you with your neck scar or a scarless neck?

Very satisfied(1) Satisfied(2) Average(3) Dissatisfied(4) Verydissatisfied(5)

Q2. How satisfied are you with the contour of your neck?

Very satisfied(1) Satisfied(2) Average(3) Dissatisfied(4) Verydissatisfied(5)

Q3. Do you think others look at your neck scar?

Absent (0) Sometimes (1) Frequent (2) Always (3)

Q4. Do you try to conceal your scar?

Absent (0) Sometimes (1) Frequent (2) Always (3)

Q5. Does your neck scar influence your choice of clothes?

Absent (0) Sometimes (1) Frequent (2) Always (3)

Q6. How often do you think about your scar?

Absent (0) Sometimes (1) Frequent (2) Always (3)

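### The printed means, SDs and 80% power need about 17 patients per group, not the stated 36, and the protocol does not show which figure is wrong

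*Protocol*

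**What the plan says.** The sample size paragraph appears with the same figures in Section 11 (Statistical analysis) and in the Statistical Analysis Plan row of the synopsis. The type I error "was set to be 0.05 on both sides" and power "was selected as 0.8 (ie, type II error" 0.2). One pair of values is 5.54 ± 1.75, introduced only by the words "The sum standard deviation is", with no arm named. The other pair, 3.92 ± 1.41, is assigned to the experimental group. Allocation is 1:1, and "the sample size calculation formula is based on the mean comparison of the two samples". The reported result from PASS is that "this study requires a sample size of about 72 people (36 cases in each group". A 10% dropout allowance then gives 40 per group, 80 in total. For the analysis itself, the same section says "Comparison between groups was performed using the Mann-Whitney U test".

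**The concern.** Every quantity that a two-sample calculation needs is printed, so the stated sample size should follow from it. A difference of 1.62 against SDs of 1.75 and 1.41 is about one standard deviation, and an effect of that size does not need 36 per group at 80% power.

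This paragraph is the only justification for enrolling 80 patients, and it concerns the primary outcome. As it stands, a reader cannot tell whether the trial was designed to detect 1.62 points or about 1.06, with what SD, or at what power. That affects how a small or null observed difference would be read.

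**Working it through.** **Inputs (Section 11, repeated in the synopsis).** Two-sided alpha 0.05; power 0.80; means 5.54 and 3.92; SDs 1.75 and 1.41; 1:1 allocation; comparison of two means. One assumption is needed: that 5.54 ± 1.75 belongs to the open group, since the other pair is labelled experimental.

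**The plan's own steps.** The dropout step reproduces: 36 / (1 − 0.10) = 40. The 36 does not.

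**Effect size.**
- Difference: 5.54 − 3.92 = 1.62
- Pooled SD: √((1.75² + 1.41²)/2) = √(5.0506/2) = 1.589
- Standardised effect: 1.62 / 1.589 = 1.019

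**Required n per group at 80% power.**
- Normal approximation: n = (1.75² + 1.41²)(1.96 + 0.8416)² / 1.62² = 5.0506 × 7.849 / 2.6244 = 15.1, so 16
- t test (noncentral t): 16.1, so 17, with power 82.2% at 17. Welch's test also gives 17.
- Mann-Whitney, 6,000 simulated trials per setting; the distribution shapes are assumptions:

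| Assumed shape | n = 16 | n = 17 | n = 18 | n = 36 |
|---|---|---|---|---|
| Normal | – | 79.8% | 81.1% | 98.5% |
| Integer score, floor 2 | – | 78.2% | 81.4% | 98.5% |
| Skewed gamma, floor 2 | 81.5% | 84.3% | – | 99.3% |

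The floor of 2 is the lowest total possible in Appendix 1: two items score at least 1 and four score at least 0. Dividing 17 by the Mann-Whitney relative efficiency instead gives 17 / 0.955 = 17.8 (18) under normality, and 17 / 0.864 = 19.7 (20) in the worst case.

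After 10% dropout, 17 / 0.9 = 18.9 (19) and 18 / 0.9 = 20, against the stated 40.

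**Power at the stated n.** With 36 per group: 98.9% (t and Welch), 99.1% (normal approximation).

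**What would make 36 the 80% figure (t test).** The standardised effect must be 0.6696. That is a difference of 0.6696 × 1.589 = 1.06 at the printed SDs, or a common SD of 1.62 / 0.6696 = 2.42 at the printed difference.

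**Other readings of the printed SDs (t test, 80% power, difference 1.62).**

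| Common SD used | n per group |
|---|---|
| 1.41 | 13 |
| 1.75 | 20 |
| √(1.75² + 1.41²) = 2.247 | 32 |
| 1.75 + 1.41 = 3.16 | 61 |

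Tightening two-sided alpha to 0.025 or 0.01 with the pooled SD gives 20 or 25. None of these is 36.

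**The case against.** Three routes to a figure near 36 can be put forward.

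- **Power of 99%.** The normal formula then gives 35.4, so 36. But the protocol states 0.8, so this would explain how the error arose without removing it.
- **A total read as a per-group number.** A Mann-Whitney calculation gives 18 per group, 36 in total. This is plausible, but it is again an error.
- **Summed variances with worst-case Mann-Whitney efficiency.** An SD of 2.247 and an efficiency of 0.864 give 31.2 / 0.864 = 36.1 (37) by t test, or 35 by the normal formula. This comes close but does not give 36, and it uses an SD that is wrong for the comparison.

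It can also be said that the matter is minor: on the printed figures the trial is not underpowered, and neither enrolment nor analysis changes. That stands for the case in which the inputs are right. There is no direct evidence that a mean or SD is misprinted, so that branch is a possibility, no more likely on the evidence than a wrong power or a wrong n. It also stands that the 16 at the bottom of the Mann-Whitney range comes only from the skewed shape, and that assigning 5.54 ± 1.75 to the open group is an inference. None of this brings the stated power and sample size into agreement.

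**Conclusion.** The sample size statement is wrong as written. On the printed inputs, 80% power needs 17 per group by t test (about 16 to 18 by simulated Mann-Whitney, at most 20 under a worst-case efficiency allowance), against 36 stated. At 36 per group, power is about 99%. The gap is a factor of about two, too large for rounding or for the word about in the text.

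The document does not settle whether the power, the sample size or an input is at fault. If the inputs are right, the error is conservative. If they are misprinted, the power for the effect really expected is unknown. The conclusion rests on reading 5.54 ± 1.75 as the comparator arm; with equal allocation, swapping the two arms would not change the sample size. The Mann-Whitney simulation figures also rest on the assumed distribution shapes.

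**What to change.** Re-run the calculation. Report the PASS procedure and the values actually entered, name the arm for 5.54 ± 1.75, and make inputs, power and sample size agree in both Section 11 and the synopsis.

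- **If the printed inputs are right,** keep 40 per group and restate the justification along these lines: 36 evaluable patients per group give about 99% power for a difference of 1.62 (SDs 1.75 and 1.41), or 80% power for a difference of about 1.06.
- **If an input was misprinted,** print the true values. As a check, 36 per group at 80% power should correspond to a standardised effect of about 0.67. The inputs should come from the original calculation and not be chosen to meet that value.

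The cost is one re-run and rewording one paragraph in two places. No extra patients are needed.

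### Patients choose their operation and rate their own scar, yet the only between-group tests the protocol states are unadjusted, although age and sex are recorded

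*Protocol*

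**What the plan says.** The synopsis gives a comparative aim: the study "is to compare the cosmetic outcomes and efficiency of retro - auricular single - site endoscopic thyroid lobectomy" and central lymph node dissection against conventional resection. Its Masking and Allocation row reads "None (Open Label). Non-Randomized(patient decided his surgery approach".

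Section 7 sets the primary outcome as "postoperative cosmetic satisfaction scores 3 months from surgery". Appendix 1 shows that the patient answers the questionnaire; its first item is "How satisfied are you with your neck scar or a scarless neck". Section 7 also lists the baseline variables: "Gender, Age, BMI, Tumor size, Pathological type, Tumor location, ASA grade".

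Section 1 remarks that "the change of aesthetic makes young women pursue a scarless neck".

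Section 11 states the method for quantitative data as "Comparison between groups was performed using the Mann-Whitney U test", and chi-square or Fisher's exact test for categorical data. The same text stands in the synopsis row titled Statistical Analysis Plan. Regression, stratification, matching and weighting are planned nowhere; matching and propensity scores occur only in titles of cited papers. Section 11 adds that a statistical analysis plan is to be written once the protocol and case report form are complete.

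**The concern.** With allocation by choice, the groups can differ before surgery in ways that also shape the answers to the questionnaire. The protocol names one such route: young women want a scarless neck, which is what the retro-auricular operation offers. If that wish also affects how a patient judges her scar or neck contour, an unadjusted comparison mixes the effect of the operation with the make-up of the groups.

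The bias could run either way. Patients who care most about scars may be harsher judges, or may be more pleased because they got what they sought. A difference on the primary score, or the lack of one, could therefore be partly due to selection. The point is confined to the cosmetic satisfaction score.

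**Working it through.** **1. The protocol's own figure.** Inputs from section 11: means 5.54 and 3.92, SDs 1.75 and 1.41, two-sided alpha 0.05, power 0.80. The sentence does not say which group 5.54±1.75 belongs to; the open group is assumed.

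- Difference = 5.54 − 3.92 = 1.62
- Pooled SD = √((1.75² + 1.41²)/2) = 1.589; standardised difference = 1.62/1.589 = 1.019
- n per group = 2 × (1.960 + 0.842)² × 1.589²/1.62² = 15.1, so 16 (17 on the t distribution)

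The stated 36 per group is not reproduced; with these inputs it corresponds to about 99% power. That is a separate matter. It is relevant here only because 36 leaves room for an adjusted analysis. The dropout step does reproduce: 36/0.9 = 40.

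**2. How large could the bias be?** The documents give no imbalance and no correlation, so everything in this step is an illustration. Assume that an underlying driver of choice differs by *s* SD between groups and correlates *r* with the score, that the operation has no effect, that the SD is 1.75 in both groups, and that 36 per group are analysed.

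- Bias = s × r × 1.75
- SE = 1.75 × √(2/36) = 0.412

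| s / r | Bias (points) | Share of 1.62 | Rejection, normal approximation | Mann-Whitney, simulated |
|---|---|---|---|---|
| 0.5 / 0.2 | 0.18 | 11% | 7% | about 6% |
| 0.8 / 0.3 | 0.42 | 26% | 17% | about 16% |
| 1.0 / 0.5 | 0.88 | 54% | 56% | about 52% |

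The simulation used whole-number scores with a floor of 2. That floor assumes the six items are summed; Appendix 1 gives no scoring rule. Without confounding, Mann-Whitney rejected in 4.7% of runs and the adjusted model in 4.2%.

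**3. How much would adjustment remove?** If the recorded covariates correlate ρ with the driver, the share of bias removed is ρ²: 9%, 25% and 49% for ρ = 0.3, 0.5 and 0.7. Simulated rejection by the adjusted model, for the three rows above in order:

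- ρ = 0.3: 5.7%, 12.3%, 43.1%
- ρ = 0.5: 5.3%, 10.2%, 29.9%
- ρ = 0.7: 4.3%, 7.5%, 15.8%
- ρ = 1.0: 4.8%, 5.1%, 4.9%

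Part of the fall comes from the larger standard error of the adjusted estimate, not from bias removal alone.

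**4. With a true difference of 1.62.** In the strongest scenario (1.0 / 0.5, ρ = 0.5) the unadjusted estimate averages 0.88 or 2.22 depending on the direction of the bias. The adjusted one averages 1.09 or 2.05: closer to 1.62, but still off.

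**5. Cost in precision.** Let R² be the share of group membership explained by two covariates. SE factor = 1/√(1 − R²). Power is from the noncentral t with 68 df and noncentrality 1.019 × √(36(1 − R²)/2).

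| R² | SE factor | Power at 36 per group |
|---|---|---|
| 0 | 1.00 | 0.99 |
| 0.1 | 1.05 | 0.98 |
| 0.2 | 1.12 | 0.97 |
| 0.3 | 1.20 | 0.95 |
| 0.4 | 1.29 | 0.91 |
| 0.5 | 1.41 | 0.85 |

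Power stays above the planned 0.80 throughout.

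**6. When adjustment could do harm.** If age and sex drive the choice but have no effect on the score, adjusting for them multiplies any bias from unmeasured preference by 1/(1 − R²): 1.11, 1.25, 1.43 and 1.67 at R² = 0.1, 0.2, 0.3 and 0.4. In a check under assumed inputs, this amplification appeared only when their effect on the score was close to zero.

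**The case against.** The strongest reply is that covariate adjustment belongs in the statistical analysis plan, which section 11 promises and which is not shown. The protocol does not rule adjustment out, and it labels no test as the primary analysis. This would settle the matter if the protocol were silent. It is not: it states its between-group tests twice, and all are unadjusted. A later plan could add adjustment, but nothing in this text calls for it.

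Second, the Mann-Whitney sentence follows directly on the one about non-normal data and may apply only there. That is a fair reading, but then no test is named for normal data and still nothing is adjusted.

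Third, the Background links age and sex to preference, hence to choice; no passage says that either affects the score within an operation. This stands. It is why the benefit of adjustment is uncertain, and why the amplification in step 6 has to be disclosed.

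Fourth, regression on age and sex does not touch expectation in open-label self-rating, and cosmetic preference itself is not recorded. This stands too, and limits what the change can achieve.

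Fifth, the linear model is one choice among several; ordinal models, stratification or weighting would also answer the point. Agreed.

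A reader might infer from the 52% figure that the planned test is likely to give a false positive. The documents do not support that: the imbalance and correlation behind it are assumed, and the mild scenario gives about 6%, close to nominal. Nor is it true that only a perfectly measured driver restores the 5% level; in the mild scenario imperfect covariates already give 5.3% and 4.3%.

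**Conclusion.** The point holds as a cheap improvement that should be made. The textual facts are firm: choice of operation by the patient, a self-rated primary outcome, recorded age and sex, a stated link between these and the wish for a scarless neck, and only unadjusted tests. Confidence in them is high.

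Confidence in how much bias adjustment would remove is moderate. Neither the size nor the direction of the bias follows from the documents, and every bias and rejection figure above rests on assumed inputs. The power range of 0.99 to 0.85 uses the protocol's means and SDs, but assumes that 5.54±1.75 is the open group and that R² lies between 0 and 0.5.

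Two stronger conclusions may tempt a reader: that the comparison is known to be biased in favour of the endoscopic operation, and that adjusting for age and sex would make it causal. The documents support neither.

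**What to change.** State as the main comparison of the 3-month cosmetic satisfaction score a prespecified model with group, age and sex, for example linear regression with robust standard errors. Report the adjusted difference with its 95% CI. Other listed pre-operative variables such as BMI may be added if named in advance. Keep the unadjusted test as supportive and show both estimates side by side. Word the conclusion as an association with residual confounding. Make the same change in section 11 and in the synopsis, and carry it into the statistical analysis plan.

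The cost is wording only, since age and sex are already collected. The downsides should be stated with the change:

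- Control is partial and may be small, because cosmetic preference is not recorded and open-label expectation remains.
- If few young women choose open surgery, overlap is poor and the estimate leans on the model's form.
- Precision falls as the covariates predict the choice.
- If age and sex affect choice but not the score, adjustment can modestly amplify bias from unmeasured preference. This is the reason to show both estimates.
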